1.4 Study Design

This is multi-center two stage phase 2 study to evaluate the clinical activity of retifanlimab in patients with unresectable or metastatic ASQ. This study will enroll subjects who have progressed after at least 1 prior chemotherapy regimen, have been deemed unfit for cytotoxic chemotherapy or who have refused cytotoxic chemotherapy. The primary endpoint of this study will be disease control rate (DCR) at 4 months following the start of treatment using RECIST 1.1. Up to 25 subjects will be enrolled to target 21 evaluable patients.

The study will consist of a screening period (within 21 days of first dose), a treatment period per the table below (**Section 10**), and a follow-up period. Subjects will receive a baseline biopsy and then be treated with the anti-PD1 antibody retifanlimab every 4 weeks. After 2 doses (8 weeks), subjects will be assessed for response with imaging and laboratory tests and receive another research biopsy. For patients with stable disease or tumor response and clinical benefit, retifanlimab will be continued until disease progression or unacceptable toxicity. Patients will be evaluated radiographically after every 2 doses of retifanlimab (every 8 weeks). Subjects will come

to the clinic for dosing and assessments on Day 1 of each cycle. Assessment will consist of 1) physician evaluation to assess symptoms of tumor response or progression and potential drug related toxicity, 2) cross sectional imaging (CT scans), 3) CA19-9 blood levels. Additional visits for safety and immune monitoring follow-up will occur per the study calendar in **Section 10**.

No dose escalations or reductions are allowed. Enrollment will continue until 21 subjects have received at least one dose of retifanlimab and completed one cycle of therapy. The null hypothesis that the DCR 4 months following the start of treatment is 5% will be tested against a one-sided alternative (DCR of 30%).

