6. DOSE MODIFICATION, DELAYS AND TOXICITY MANAGEMENT GUIDELINES FOR IMMUNE-RELATED AES

6.1 Dose Modifications

[figure not shown]
Subjects will be monitored continuously for AEs while on study drug. Subjects will be instructed to notify their physician immediately for any and all AEs. Dose escalations or reductions of retifanlimab will not be allowed.

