13. STATISTICAL CONSIDERATIONS

13.1 Study Design/Endpoints

Sample Size calculation and justification

Simon's two-stage optimal design will be used ¹⁸. The null hypothesis that the true disease control rate at 4 months is 5% will be tested against a one-sided alternative of 30% disease control rate at 4 months. In the first stage, 7 patients will be accrued. If there are zero patients with disease control by 4 months, the study will be stopped. Otherwise, 14 additional patients will be accrued for a total of 21 patients. The null hypothesis (disease control rate of 5%) will be rejected if 3 or more patients with disease control at 4 months are observed in stage 1 and 2 combined. This design yields a type I error rate of 0.064 (target type I error 0.1) and power of 90% when the true disease control rate is 30%. The probability of stopping the trial early for futility is 70% if the true DCR is 5%.

We plan to enroll 25 subjects to ensure 21 would be evaluable for DCR. As this is a rare tumor subtype patients will be recruited at several sites including Johns Hopkins Hospital, Memorial Sloan Kettering Cancer Center and the Mayo Clinic. We do not anticipate any difficulties in trial enrollment. We expect an accrual rate of at least 2 patients per month across the sites, completing trial enrollment in 12 months.

Patients are evaluable for DCR if they receive at least one dose of retifanlimab, and have at least one post-baseline tumor assessments or discontinue due to toxicity or clinical progression prior to post-baseline tumor assessments. The study plans to enroll 25 subjects to ensure 21 would be evaluable for the primary efficacy endpoint.

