The safety analysis will be performed in all subjects who receive at least one dose of study drug. A baseline measurement and at least 1 laboratory or other safety-related measurement obtained after at least 1 dose of study treatment may be required for inclusion in the analysis of a specific safety parameter (e.g., lab shifts from baseline). A complete list of all AE data will be provided along with an assessment of NCI CTCAE grade and relationship to study drug. The incidence of AEs will be tabulated by subgroups of interest (e.g. grade 3 or higher, organ class, relationship to study drug). For analyses at the individual level, the highest grade and relationship to study drug will be assumed if multiple events have occurred. Toxicity will be tabulated by type and grade and will be summarized with descriptive statistics. Other safety data will be assessed in terms of

physical examination, clinical chemistry, hematology, vital signs, and ECGs. Negative binomial regression and Cox proportional hazards models will be used to assess the rate of AE and time to first toxicity, respectively.

Exploratory Clinical Analysis

Overall survival is defined as the duration of time from start of study treatment to time of death. For subjects lost to follow-up or whose vital status is unknown, every effort will be made to determine the date such subjects were last known to be alive. Such efforts may include phone calls, certified mail, and the checking of public records. Subjects who are alive or lost to follow-up as of the data analysis cutoff date will be right-censored. The censoring date will be determined from the date the subject was last known to be alive.

OS will be summarized descriptively using the Kaplan-Meier method. Analysis of OS will be restricted to evaluable individuals who complete at least one dose of retifanlimab. Median event-free survival will be reported and the associated 95% confidence interval will be estimated.

DOR and TTP were defined in second 11.3.

Exploratory Biomarker Analysis

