13.3 Safety Analysis

The safety analysis will be performed in all treated subjects. AE data will be listed individually and incidence of AEs summarized by system organ class and preferred terms within a system organ class for each treatment group. When calculating the incidence of AEs, each AE (based on preferred terminology defined by CTCAE version 5.0) will be counted only once for a given subject. In analyses of grade and causality, if the same AE occurs on multiple occasions, the highest grade and strongest relationship to study drug will be assumed. If 2 or more AEs are reported as a unit, the individual terms will be reported as separate experiences.

Changes in vital signs, hematology and clinical chemistry parameters from baseline to the end of the study will be examined. Toxicity will be tabulated by type and grade. Toxicities will be characterized according to the CTCAE version 5.0. Treatment-emergent changes from normal to abnormal values in key laboratory parameters will be identified.

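### A Cox model is the only stated analysis of time to first toxicity in a one-arm, one-dose trial: it has no contrast to estimate, and no descriptive estimate of toxicity timing is planned

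*Combined protocol and SAP*

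**What the plan says.** Under the safety part of section 13.2, one sentence carries the whole model specification: "Negative binomial regression and Cox proportional hazards models will be used to assess the rate of AE and time to first toxicity, respectively". It gives no covariate, definition of toxicity, time origin, end of the risk period, rule for death or early exit, or exposure term.

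The setting is a single-arm study. Section 1.4 describes it thus: "This is multi-center two stage phase 2 study to evaluate the clinical activity of retifanlimab in patients with unresectable or metastatic ASQ". It also sets the size: "Up to 25 subjects will be enrolled to target 21 evaluable patients". Section 6.1 rules out dose groups: "Dose escalations or reductions of retifanlimab will not be allowed". Section 13.3 nevertheless asks for AE incidence "summarized by system organ class and preferred terms within a system organ class for each treatment group", although there is only one group.

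The other safety analyses in sections 13.2 and 13.3 are listings and tables by type, grade, organ class and relationship to drug. Section 11.2 does not list time to toxicity among its safety measures. Section 13.2 names Kaplan-Meier for PFS and OS but names no curve for toxicity.

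**The concern.** A Cox model is used to estimate hazard ratios between levels of a covariate. With one arm, one dose and no covariate named, it has no such parameter here. Objective 1.2.3 is to characterise the toxicity attributable to retifanlimab. Tables by type and grade show how much toxicity occurs but not when. As written, the timing has no usable planned estimate, and an analyst would have to choose the event, the risk period and the handling of death and early exit after seeing the data.

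The rate analysis has a smaller gap. Patients will be observed for different lengths of time. Without an exposure offset, a negative binomial model returns mean events per patient rather than a rate per unit time.

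**Working it through.** **The plan's own figures.** The plan gives no figure for either regression. The toxicity rate it assumes elsewhere (sections 5.6 and 13.4) is the mean of a Beta(1.5, 5.5) prior: 1.5 / (1.5 + 5.5) = 0.214, printed as 21%. The Simon design in section 13.1 (stop at 0 of 7, reject at 3 or more of 21) also reproduces: type I error 0.0639 (printed 0.064), power 90.4% (printed 90%), early stopping 69.8% (printed 70%). Neither regression enters that design.

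**1. Could a covariate be supported?** The inputs are 25 patients and the 21% prior rate, with the 33% safety boundary as an upper case. Expected first unacceptable toxicities are 25 × 0.21 = 5.25 and 25 × 0.33 = 8.25. For a hypothetical 50:50 binary covariate at two-sided 0.05, the Schoenfeld approximation gives power = Φ(√d × ln(HR) / 2 − 1.96).

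- HR 2, d = 5.25: √5.25 × 0.693 / 2 = 0.794, so Φ(−1.166) = 12%. With d = 8.25, 17%.
- HR 3, d = 5.25: 24%. With d = 8.25, 35%.
- Events for 80% power, 4 × (1.96 + 0.842)² / (ln HR)²: 66 for HR 2 and 27 for HR 3. Both exceed the number of patients.
- The 95% limits for the hazard ratio lie a factor of exp(1.96 × 2 / √5.25) = 5.5 either side of the estimate.

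The 21% refers to unacceptable toxicity only. If half of the 25 patients had an event (an assumption), d = 12.5 and power for HR 2 would still be 23%.

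**2. Does the offset matter?** In one simulated data set of 25 patients, an intercept-only negative binomial with log person-time as offset gave 0.521 events per month, against a crude rate of 0.523. Without the offset it gave 1.6, which is the mean number of events per patient.

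**3. Does the handling of exits matter?** The documents do not give the rate at which patients leave AE observation, so this is an illustration over a range. Assume constant hazards, exit hazard b = ln 2 / (exit median), and an eventual toxicity proportion of 21%, so the toxicity hazard is a = b × 0.21 / 0.79.

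- Exits treated as simple censoring: 1 − KM(t) = 1 − exp(−a t).
- Exits treated as a competing event: CIF(t) = 0.21 × (1 − exp(−(a + b) t)).

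Worked case, exit median 1.5 months: b = 0.462, a = 0.123. At 6 months, 1 − exp(−0.737) = 52% and 0.21 × (1 − exp(−3.51)) = 20%.

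| Exit median (months) | 1 − KM, 6 months | CIF, 6 months | Of 25, event-free and still observed at 6 months |
|---|---|---|---|
| 1.5 | 52% | 20% | 0.7 |
| 2.4 | 37% | 19% | 2.8 |
| 4 | 24% | 15% | 6.7 |
| 6 | 17% | 12% | 10.4 |

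The last column is 25 × exp(−(a + b) × 6). At 3 months the gap is 31% versus 17% with an exit median of 1.5 months, and 12.9% versus 10.1% with 4 months.

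**The case against.** The strongest reply is that the sentence is under-specified rather than wrong. Much of that stands.

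- An intercept-only negative binomial with an exposure offset is a valid AE rate for one arm. The fault is the missing offset, not the model.
- A Cox fit without covariates still yields a baseline cumulative hazard. A reader might infer that the stated models cannot describe toxicity timing at all; that goes too far. But the baseline hazard needs the same missing event, origin and censoring rules, and nothing says it will be reported.
- Within-arm covariates are conceivable, since objective 1.3.4 seeks predictors of autoimmune toxicity. Nothing links that objective to these models, and step 1 shows how little they could support.
- A reader might infer that the plan will overstate toxicity. The documents do not support that. They never name 1 minus Kaplan-Meier for toxicity, and they are silent on exits rather than committed to ignoring them.
- The 1.5-month exit median is the PFS of a cited trial in pancreatic ductal adenocarcinoma (section 13.1), not an exit time in this trial. Sections 5.9.1 and 13.2 allow treatment beyond first progression, section 7.5.1 follows AEs for 28 days after the last dose and longer if related, and section 5.11 adds a 90-day contact. The 52% versus 20% row is therefore one extreme.
- Stopping drug for progression does not preclude toxicity: section 6.2 says immune-related events can appear months after the last dose. Progression should not be a competing event; death clearly is.

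The tables in sections 13.2 and 13.3 do serve objective 1.2.3 for frequency and grade. What they lack is timing.

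**Conclusion.** The point holds as a wrong choice of method for one secondary safety analysis, together with a missing specification. The only stated analysis of time to first toxicity is a Cox model that has no contrast in this design. About 5 unacceptable toxicities (8 at the 33% boundary) could not support a covariate, although any-grade toxicity would give more events. No descriptive estimate of timing is planned, although Kaplan-Meier is named for PFS and OS.

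The bias from careless handling of exits cannot be fixed from the documents. It runs from 5 to 32 percentage points at 6 months over exit medians of 6 to 1.5 months, assuming constant hazards and a 21% eventual proportion. The table counts every exit as a competing event. Where patients leave observation alive, cumulative incidence with only death competing would remove only the part of the gap that is due to deaths.

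A reader might also infer that the trial's safety objective goes unanswered or that its decisions are at risk. Neither follows: the AE tables remain, and neither the DCR test nor the Bayesian toxicity rule uses these models.

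**What to change.** Replace the sentence in section 13.2 with:

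> Time from first dose to first drug-related toxicity (any grade, grade 3 or higher, and unacceptable toxicity separately) will be described by the cumulative incidence function (Aalen-Johansen) with death without prior toxicity as a competing event and follow-up censored at the end of the AE collection window, with 95% CI at 8 weeks, 4 months and 6 months. AE rates will be given per patient-month of AE observation with 95% CI from an intercept-only negative binomial model with a log person-time offset. Any covariate regression is exploratory.

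State which date closes the AE window for each event type, since section 7.5.1 uses different periods for all AEs, related AEs and SAEs. Correct the treatment-group wording in section 13.3.

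The cost is a short SAP edit and standard software. The dates needed are first dose, last dose, toxicity onset and death. The Appendix D form captures these for SAEs; confirm that the CRF records onset dates for non-serious AEs. The downside is precision: early exit will leave few patients under observation at the later time points (about 1 to 10 of 25 at 6 months in the illustration), so those intervals will be wide. Censoring at the end of the window also still assumes that those who leave are like those who stay.

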13.3 Safety Analysis

The safety analysis will be performed in all treated subjects. AE data will be listed individually and incidence of AEs summarized by system organ class and preferred terms within a system organ class for each treatment group. When calculating the incidence of AEs, each AE (based on preferred terminology defined by CTCAE version 5.0) will be counted only once for a given subject. In analyses of grade and causality, if the same AE occurs on multiple occasions, the highest grade and strongest relationship to study drug will be assumed. If 2 or more AEs are reported as a unit, the individual terms will be reported as separate experiences.

Changes in vital signs, hematology and clinical chemistry parameters from baseline to the end of the study will be examined. Toxicity will be tabulated by type and grade. Toxicities will be characterized according to the CTCAE version 5.0. Treatment-emergent changes from normal to abnormal values in key laboratory parameters will be identified.

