7.2 Assessment of Causality

The relationship of an AE to the administration of the study drug is to be assessed by the investigator according to the following definitions:

- No (unrelated, not related, no relation): The time course between the administration of study drug and the occurrence or worsening of the adverse event rules out a causal relationship and another cause (concomitant drugs, therapies, complications, etc.) is suspected.
- Yes (related): The time course between the administration of study drug and the occurrence or worsening of the adverse event is consistent with a causal relationship and no other cause (concomitant drugs, therapies, complications, etc.) can be identified.

The following factors should also be considered:

• The temporal sequence from study drug administration - The event should occur after the study drug is given. The length of time from study drug exposure to event should be evaluated in the clinical context of the event.

- Underlying, concomitant, intercurrent diseases Each report should be evaluated in the context of the natural history and course of the disease being treated and any other disease the subject may have.
- Concomitant medication The other medications the subject is taking or the treatment the subject receives should be examined to determine whether any of them might be recognized to cause the event in question.
- Known response pattern for this class of study drug Clinical and/or preclinical data may indicate whether a particular response is likely to be a class effect.
- Exposure to physical and/or mental stresses The exposure to stress might induce adverse changes in the recipient and provide a logical and better explanation for the event.
- The pharmacology and pharmacokinetics of the study drug The known pharmacologic properties (absorption, distribution, metabolism, and excretion) of the study drug should be considered.

Assessment of Grade:

The investigator will make an assessment of grade for each AE and SAE reported during the study, which will be recorded in the CRF. The assessment will be based on the National Cancer Institute's CTCAE (Version 5.0) and graded as shown below:

- Grade 1: Mild; asymptomatic or mild symptoms; clinical or diagnostic observations only; intervention not indicated
- Grade 2: Moderate; minimal, local or noninvasive intervention indicated; limiting ageappropriate instrumental activities of daily living

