11.2 Secondary Endpoints

The secondary endpoints are as follows:

- ORR is defined as the proportion of subjects with PR or CR according to RECIST 1.1. Subjects who discontinue due to toxicity or clinical progression prior to post-baseline tumor assessments will be considered as non-responders. Otherwise, subjects who discontinue or do not have any post-baseline scans for other reasons including withdrawal of consent or being lost to follow-up prior to C2D1 will be replaced and not included in the primary efficacy analysis.
- Progression-free survival (PFS) is defined as the number of months from the first
 dose of retifanlimab to radiographic disease progression (PD or relapse from CR
 as assessed using RECIST 1.1 criteria), documented clinical progression as
 assessed by the treating provider, or death due to any cause. PFS will be censored
 at the date of the last scan for subjects without documentation of disease
 progression at the time of analysis.
- Safety assessed by the following measures:
 - Number of patients who have grade 3 or above drug-related toxicities
 - Frequency of drug-related toxicity by grade
 - Retifanlimab-related infusion reactions
 - Immune-related AEs
 - Unacceptable toxicities
 - Vital signs: BP, pulse, temperature
 - Physical examination
 - Changes in ECG readings
 - Clinical hematology: complete blood count (CBC) with differential ANC,
 ALC, AEC, and platelet count
 - Clinical serum chemistry: sodium, potassium, chloride, bicarbonate, glucose, blood urea nitrogen (BUN), creatinine, lactate dehydrogenase (LDH), ALT, AST, alkaline phosphatase, lipase, bilirubin (total), total protein, albumin, calcium, magnesium and phosphate

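### For repeat adverse events, grade and causality may come from different occurrences, so the grade 3+ drug-related counts in Section 11.2 can be overstated

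*Combined protocol and SAP*

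**What the plan says.** Section 13.3 counts by preferred term: each event "will be counted only once for a given subject". For analyses by grade and causality it adds that "if the same AE occurs on multiple occasions, the highest grade and strongest relationship to study drug will be assumed".

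Section 13.2, under the safety endpoints, has a parallel sentence: "For analyses at the individual level, the highest grade and relationship to study drug will be assumed if multiple events have occurred". This one applies to the individual and is not restricted to recurrences of the same event.

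Section 11.2 lists two safety measures that need grade and causality together: "Number of patients who have grade 3 or above drug-related toxicities" and "Frequency of drug-related toxicity by grade". They serve objective 1.2.3, on treatment-related events. No other section says how to derive them.

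Section 7.2 gives causality two levels only, unrelated or related. Section 13.3 sets the population: "The safety analysis will be performed in all treated subjects". Section 13.1 plans to enrol 25 so that 21 are evaluable.

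**The concern.** Both sentences take two maxima over a set of occurrences. Neither ties them to the same occurrence, and neither selects the related occurrences before taking the grade. Because causality is binary, one related occurrence makes the whole set related, and the grade can then come from an occurrence that the investigator judged unrelated.

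At stake is the main descriptive statement about severe drug-related toxicity. In a single-arm trial of this size one patient moves the percentage visibly, and there is no comparator in which the same inflation would cancel.

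The two sections also differ in scope. Section 13.3 collapses within one event term; Section 13.2 does not say so. Two programmers could follow different sentences and report different counts from the same data.

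**Working it through.** The plan states no figure that depends on this rule, so there is none to reproduce. The check applies the written rule to a defined case, settles the direction of any error, and sizes it per patient.

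**1. The two counting rules.** Let occurrence *i* of one event term in one patient have grade *g_i* and relationship *r_i* (1 = related, 0 = unrelated; Section 7.2).
- As written in 13.3: count as grade 3+ drug-related if max(*g_i*) ≥ 3 and max(*r_i*) = 1.
- Same-occurrence rule: count only if some *i* has *g_i* ≥ 3 and *r_i* = 1.

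**2. A mixed case.** Same event, two occurrences:

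| Occurrence | Grade | Related |
|---|---|---|
| First | 1 | yes |
| Second | 3 | no |

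As written: highest grade 3, strongest relationship related, so the patient counts (1). Same-occurrence rule: no occurrence is both, so the patient does not count (0).

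**3. Direction.** With no related occurrence, both rules exclude the patient. With at least one, the written rule takes the highest grade over all occurrences and the alternative takes it over the related ones only. A maximum over a subset cannot exceed the maximum over the whole set. The written rule therefore never gives a lower grade. The grade 3+ count can only rise, and the by-grade table can only shift towards higher grades.

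**4. Size per affected patient.** 1/25 = 4.0 percentage points if all 25 planned patients are treated; 1/21 = 4.8 if 21 are. Two patients of 25 give 8.0 points and three give 12.0.

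**5. Illustration for the same-event rule.** The documents give neither input, so both are assumptions: *c*, the true proportion with a grade 3+ related event (10% to 21%), and *m*, the share of the remaining patients who show the mixed pattern (2% to 10%).

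Reported proportion = *c* + *m*(1 − *c*); expected extra patients of 25 = 25*m*(1 − *c*).

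| *c* | *m* | Reported | Extra of 25 |
|---|---|---|---|
| 0.10 | 0.02 | 0.118 | 0.45 |
| 0.10 | 0.10 | 0.190 | 2.25 |
| 0.21 | 0.02 | 0.226 | 0.40 |
| 0.21 | 0.10 | 0.289 | 1.98 |

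Under these assumptions, between about 0.4 and 2.3 extra patients are expected. At the low end the realised number may well be zero.

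**6. What the rule does not reach.** The disease control rate (13.1, 13.2) uses no adverse event data. The stopping guideline (5.6, 13.4) counts unacceptable toxicities by the Section 5.6 event definition, not by the collapsing rule.

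**The case against.** **The rule may be meant for one-way tables.** Highest grade would then serve the grade tables and strongest relationship the causality tables. The wording allows this but does not say it. If it is the intent, the two joint endpoints in 11.2 have no derivation, and the same clarification is needed.

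**Section 11.2 already describes an event-level count.** A patient with no toxicity that is both severe and related arguably does not meet it. That is a fair reading, but nothing says that it overrides the collapsing rules in Section 13.

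**The mixed pattern may be rare.** Section 7.1.1 reports a grade 1 or 2 laboratory abnormality as an adverse event only if it is clinically significant, is serious, or leads to interruption or discontinuation of study drug. A plain grade 1 ALT rise would therefore often be absent from the data. The same section does not record expected progression of the cancer. Section 7.5.1 stops following unrelated events 28 days after the last dose, although serious events are collected for longer. These limits stand. They reduce the likely number of affected patients but do not make it zero.

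**The rule is prespecified, conservative, and recoverable from listings.** It cannot hide a safety signal, and the individual listings carry each event's grade and relationship. This lowers the severity of the point. It does not correct the tabulated endpoint, and a recount chosen after seeing the data would be post hoc.

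**A stronger reading is tempting.** A reader might take 13.2 to merge different events in one patient, so that a mild related rash and an unrelated severe pain become one severe related toxicity. Suppose 10% truly have a grade 3+ related event and, independently, shares *a* and *b* of the others have a low-grade related and a severe unrelated event. The reported rate is then 0.10 + 0.90*ab*: 0.181 at *a* = *b* = 0.3 and 0.325 at *a* = *b* = 0.5, or about 2 to 6 extra patients of 25. The documents do not support this as a finding. Every input is assumed. Section 13.2 itself goes on to tabulate toxicity by type and grade, 13.3 confines collapsing to the same event, and pain from expected progression may not be recorded at all.

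**Conclusion.** The point holds for repeat occurrences of the same event. As written, Section 13.3 can label a patient grade 3+ drug-related when no single occurrence was rated so, and the looser wording of 13.2 adds uncertainty about scope. The error in the two joint endpoints of 11.2 runs upward only, by 4 percentage points per affected patient with 25 treated.

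The number affected cannot be found from the documents; zero to a few is a reasonable expectation. The range of 0.4 to 2.3 rests wholly on assumed frequencies. Larger figures depend on merging different event terms under 13.2 and are hypothetical.

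A reader might also infer that the trial's conclusion or its safety stopping is compromised. Neither follows: only descriptive secondary safety tables are involved. The point is moderate, not a must-fix.

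**What to change.** Use one rule in Sections 13.2 and 13.3 and for the two endpoints in 11.2:

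> For drug-related tables, restrict to occurrences rated related, then take the highest grade among those. For all-cause tables, take the highest grade over all occurrences.

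In 13.2, also limit collapsing to the same event term for term-level tables. For the patient-level endpoint it follows that a patient counts if at least one occurrence is rated both related and grade 3 or above.

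The cost is a few sentences of text and one filter in the table programs, applied before the maximum is taken. No new data are needed, because the planned listings already hold grade and relationship for each event. The one downside is that the reported drug-related grade 3+ count becomes less conservative. The all-cause tables will still show every severe event.
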